**A: Specific Aims**

**Aim 1:** To determine if blue light therapy is superior to 5% topical benzoyl peroxide gel in eradicating *Cutibacterium Acnes* at the deltopectoral interval of the shoulder

**Aim 2:** To determine if blue light therapy has additive or synergistic effects in eradicating *Cutibacterium Acnes* in conjunction with 5% topical benzoyl peroxide gel at the deltopectoral interval.

**Hypothesis:** Blue light therapy will result in fewer positive culture specimens than those treated with topical benzoyl peroxide for *Cutibacterium Acnes*

**B: Purpose**

Infection after shoulder surgery leads to significant morbidity to patients and puts significant strain on the healthcare system. As the case volume of shoulder arthroplasties continues to rise, the importance of minimizing infection rises in concert. The purpose of this study is to determine if blue light therapy, used commonly in dermatologic practice, is as effective as or more effective

than 5% topical benzoyl peroxide gel in reducing the incidence of positive cultures for *Cutibacterium Acnes*.

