In recent years, topical methods of eradicating or reducing the skin burden of *C. Acnes* have been investigated, including chlorhexidine swabs and topical benzoyl peroxide (BPO) as oral antibiotics including doxycycline have not proven effective. Topical BPO has been shown in several studies to be superior to chlorhexidine in reducing bacterial load using swab cultures of the epidermis and deep sebaceous glands. However, several drawbacks of topical BPO have been described including bleaching of clothing, requirement for serial application leading to poor compliance, potential for irritant and allergic contact dermatitis, and inconsistency in eradicating *C. Acnes* in some reports. In addition, there is concern that topical treatments may not penetrate into the superficial dermal layers to eradicate bacteria colonizing 1 mm beneath the skin surface, where the sebaceous glands reside.

Blue light therapy, with wavelength 405nm-470 nanometers (nm), is an Food & Drug Administration (FDA) approved modality that has previously been described in the dermatology literature as a highly effective antimicrobial agent against *C. Acnes*, among other bacteria, in mild to moderate inflammatory acne patients. The benefit of blue light therapy is that a single treatment can kill 99.9% of *C. Acnes*. The anti-microbial mechanism of action involves absorption by endogenous porphyrins which induce generation of reactive oxygen species leading to cell death and DNA cleavage. In contrast to topical antimicrobials, blue light therapy penetrates to 1.2-1.5 mm beneath the skin surface to eliminate bacteria residing in the sebaceous glands. Blue light demonstrates bactericidal effects at doses as low as 5 J/cm^2, while higher doses (>100 J/cm^2) are necessary to injure human tissues. Wavelengths of 405-415 nm with a radiant exposure of 54 - 75 J/cm^2 have been demonstrated to exert the greatest antimicrobial effects against *C. Acnes*. Variables that affect radiant exposure include: power of the blue light device (W), desired surface area to be treated (cm^2), time duration of treatment (s). Devices with lower irradiances (W/cm^2) require treatment for a longer time duration (s) to

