#### **Future Directions:**

- Subsequent investigations to evaluate the efficacy of blue light therapy for eradication of *C. Acnes* will include a randomized clinical trial in shoulder arthroplasty patients incorporating not only superficial cultures but deep cultures and synovial fluid analysis.
- Additional studies targeting the highest risk surgical patient population, revision arthroplasty cases, will be impactful. These studies should incorporate 2-year clinical follow-up complete with patient reported outcome measures to see if utilization of blue light therapy may be associated with diminished pain and dysfunction in those patients with culture negative work-up.
- Finally, blue light studies to date indicate promising applications beyond *C. Acnes* including activity against staph, strep, pseudomonas, and yeast. Future studies could focus on these species as sources of both prosthetic joint infection as well as blue light's role in treatment and preventing infection across multiple specialties.

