#### **E: Research Design and Methods**

**Study Design:** Single-Blinded (investigators performing analysis), randomized controlled trial

**Study Participants/Human Subjects:** 60 volunteers

**Power Analysis:** Power analysis calculations were performed using G\*Power (Universität Kiel, Germany). With an  $\alpha$  of 0.05 and 90% power to detect a 50% difference in positive culture rates as previously described, it was determined that 51 total patients needed to be enrolled. For the purposes of the present study, assuming a 15% attrition rate, it was determined that 20 subjects per group, 60 subjects total, were necessary.

**Inclusion Criteria:** Healthy Male Volunteers at least 18 years of age

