#### **Randomized Groups:**

- N=20
  - 5% Topical Benzoyl Peroxide Gel + 2% Chlorhexidine Gluconate with 70% Isopropyl Alcohol. Contralateral shoulder serving as control (2% Chlorhexidine Gluconate with 70% Isopropyl Alcohol only)
- N=20
  - Blue Light Therapy + 2% Chlorhexidine Gluconate with 70% Isopropyl Alcohol. Contralateral shoulder serving as control (2% Chlorhexidine Gluconate with 70% Isopropyl Alcohol only)
- N=20
  - 5% Topical Benzoyl Peroxide Gel + Blue Light Therapy + 2% Chlorhexidine Gluconate with 70% Isopropyl Alcohol. Contralateral shoulder serving as control (2% Chlorhexidine Gluconate with 70% Isopropyl Alcohol only)
- In addition to randomizing subjects to one of the 3 above groups, subjects will be randomized to have either their right or left arm as the “treatment” arm with the contralateral serving as control. Within each group of 20 subjects, 10 will be randomized to having the right arm as the “treatment” arm and 10 will be randomized to having the left arm as the “treatment” arm.
  - Randomization will be performed using concealed envelopes to be picked at random once a subject is consented for participation in the study.

- The research coordinator consenting subjects and coordinating the blue light treatment will not be blinded given their involvement. The remainder of the research team will be blinded to both treatment arm as well as which side (left or right) served as the control.
- **Figure 1** below details the 3 separate groups that subjects could be randomized to. Each of the 3 groups will contain 20 subjects. Within each of the 3 groups, subjects will be randomized to having either the right or the left arm being the treatment arm. The treatment arm means that arm will receive either 5% topical benzoyl peroxide, blue light therapy, or both. The contralateral shoulder will be the control for each subject.

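### The Purpose asks whether blue light is as effective as BPO or better, but Aim 1, the Hypothesis and the sample size address only a difference, and no margin or parity test is given.

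*Combined protocol and SAP*

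**What the plan says.** All references are to the combined protocol and SAP.

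- **B: Purpose**, with 5% topical BPO gel as the comparator and positive *C. acnes* cultures as the outcome, sets an either/or question: "The purpose of this study is to determine if blue light therapy, used commonly in dermatologic practice, is as effective as or more effective".
- **A: Specific Aims, Aim 1** is superiority only: "To determine if blue light therapy is superior to 5% topical benzoyl peroxide gel in eradicating" *C. acnes*. The **Hypothesis** has the same direction: "Blue light therapy will result in fewer positive culture specimens than those treated with topical benzoyl peroxide for" *C. acnes*.
- **E: Research Design and Methods, Power Analysis** uses an alpha of 0.05 and "90% power to detect a 50% difference in positive culture rates as previously described", from which "it was determined that 51 total patients needed to be enrolled". Allowing for 15% attrition, this becomes 20 per group and 60 in total. The test, its sidedness, the comparison and the rates per group are not stated.
- **Randomized Groups** adds a within-person comparator: "The contralateral shoulder will be the control for each subject".

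The text contains no statistical analysis section, no non-inferiority or equivalence margin, no confidence-interval rule, and no statement that the Aims take precedence over the Purpose.

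**The concern.** The two statements of the study question give opposite answers to the same result. If blue light and BPO do not differ significantly, Aim 1 has failed. Under the Purpose, the same result could be presented as showing that blue light works as well as BPO.

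That reading would be attractive here. The Background section says that "several drawbacks of topical BPO have been described including bleaching of clothing, requirement for serial application leading to poor compliance", whereas blue light is given as one session at the visit. A reader could be content with parity and regard the trial as having shown it.

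Parity needs a margin and enough precision to exclude it, and the plan gives no margin. What is at stake is the conclusion that is reported and carried into later work, which according to Future Directions "will include a randomized clinical trial in shoulder arthroplasty patients". This is a skin-culture study in healthy volunteers, so their safety is not affected.

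**Working it through.** **1. Reproduce the plan's sample size.** Inputs from the Power Analysis: alpha 0.05, power 90%, a 50% difference, 51 evaluable, 15% attrition.

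- *Three-group chi-square*, inferring effect size w = 0.5 and 2 degrees of freedom, with noncentrality N × w²: power is 0.896 at N = 50 and 0.902 at N = 51. This gives 51.
- *Pairwise test of two proportions*, two-sided: n per arm = [1.96 √(2p̄(1−p̄)) + 1.2816 √(p₁(1−p₁) + p₂(1−p₂))]² / (p₁−p₂)². For 60% vs 10%, p̄ = 0.35, so n = [1.96 × √0.455 + 1.2816 × √0.33]² / 0.25 = 16.95, or 17 per arm, and 3 × 17 = 51. By symmetry, 90% vs 40% gives the same. For 75% vs 25% the answer is 19 per arm.
- *Attrition*: 51 / 0.85 = 60.

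The origin of 51 is therefore ambiguous, but every route found that reproduces it is a test of difference.

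**2. How often would a real deficit be non-significant?** The documents give no rates and name no test. Assumptions: two independent groups, one positive/negative result per subject, two-sided 0.05, and blue light truly worse. The lower (BPO) positive rate is 10–50%, or 10–40% for the 50-point deficit. All 2×2 tables were enumerated exactly.

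| True deficit | 20 per arm: Fisher / chi-square | 17 per arm: Fisher / chi-square |
|---|---|---|
| 20 points | 76–86% / 64–78% | 81–86% / 70–77% |
| 30 points | 51–66% / 38–55% | 61–69% / 47–55% |
| 50 points | 9–17% / 5–10% | 17–21% / 10–12% |

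Non-significance is thus some evidence against a deficit near 50 points, but little against one of 20 to 30.

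**3. What would identical observed results show?** Newcombe 95% CI for the difference, 20 per arm:

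- 2/20 vs 2/20: ±21 points
- 5/20 vs 5/20: ±26 points
- 10/20 vs 10/20: ±28 points

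Even a perfect tie does not exclude a 20-point deficit.

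**4. What margin could the trial support?** With equal true rates p, one-sided 0.025 and 90% power, the smallest margin is (1.96 + 1.2816) × √(2p(1−p)/n).

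- n = 20: p = 0.10 gives 3.2416 × √(0.18/20) = 0.31; p = 0.50 gives 3.2416 × √(0.50/20) = 0.51.
- n = 17: the same formula gives 0.33 and 0.56.

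**5. What would a 20-point margin need?** n per arm = (1.96 + 1.2816)² × 2p(1−p) / 0.20². For p = 0.10 this is 10.51 × 0.18 / 0.04, or 48. For p = 0.50 it is 10.51 × 0.50 / 0.04, or 132. At 15% attrition, 48/0.85 = 57 and 132/0.85 = 156 enrolled per arm, against 20 planned. The 20-point margin is illustrative.

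**The case against.** The strongest reply is that the formal Aim and Hypothesis both state superiority, and that the phrase in the Purpose is one introductory sentence, possibly loose idiom. That is fair, and it makes the harm conditional. It does not remove the mismatch: the phrase is the stated purpose, and nothing says which wording governs.

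Three stronger readings are tempting, and the documents do not support them.

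- *The investigators plan to call non-significance parity.* Nothing says so. The wording only leaves it open.
- *The trial was sized on a three-group test and so not for blue light against BPO.* The figure of 51 fits that test, but it also fits 17 per arm in a pairwise comparison of 60% vs 10% or 90% vs 40%. The basis is unknown, and a pairwise one is not ruled out.
- *The design cannot support parity at all.* That depends on the margin, the rates and the analysis. Twenty per arm could support margins of about 31–51 points. These are wide, but the plan gives no margin to judge them against. Using the contralateral shoulder or colony counts could also change the precision.

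It is also fair that every probability above rests on assumed rates and an assumed test. They show scale and do not predict this trial's results.

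**Conclusion.** The point holds as an internal inconsistency in the study question. The mismatch and the absence of a margin are read directly from the text and depend on no assumption. The sample-size arithmetic is not in dispute, since 51 and 60 both reproduce.

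The quantitative conclusion is narrower. Under an unpaired binary analysis at 17–20 per arm, with rates of 10–50% and two-sided 0.05, a parity claim at margins of about 20 points or less is not supportable. The effect is on what may be concluded and reported. It is worth correcting before the results are analysed.

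**What to change.** Restate the Purpose as superiority, in line with Aim 1. For example: *The study asks whether blue light lowers the proportion of C. acnes-positive cultures more than 5% BPO gel does.* Then add: *A non-significant difference between blue light and BPO will be reported with the 95% CI for the difference in positive-culture rate, as superiority not shown, and will not be reported as equal efficacy.*

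The cost is two sentences of protocol text, with no extra subjects or data. The sponsor gives up a parity claim.

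The added sentence belongs to the superiority route only. Under a non-inferiority analysis, a non-significant difference whose CI excludes the margin would be a success, so the sentence would conflict with it. If the sponsor wants the parity question, it must instead pre-specify a justified margin and a CI-based test, and restate what the sample size can deliver. The sizes in step 5 of the working show that this is not a cheap change.

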### **C: Background & Significance**

*Cutibacterium Acnes* (*C. Acnes*), formerly known as *Propionibacterium Acnes*, is a common pathogen leading to infection following shoulder surgery. *P. Acnes* a gram-positive, facultative anaerobic rod that resides in the pilosebaceous ducts of the skin and has a predilection for colonizing the skin of human shoulders more frequently than at the hip or knee region. A recent investigation characterizing the shoulder microbiome reported no evidence of *C. Acnes* in any subdermal tissues including subcutaneous fat, rotator cuff tendon, joint capsule, and cartilage indicating *C. Acnes* is solely a skin flora. Surgical site infection can be a devastating complication of shoulder surgery, particularly arthroplasty surgery, leading to pain, future surgeries, and significant health care costs. In revision shoulder arthroplasty cases, *C. Acnes*, has been identified as one of the most common pathogens with rates ranging from 19% to 70% of cases performed for prosthetic joint infection (PJI). Risk factors for infection after shoulder surgery, including *C. Acnes*, includes male gender, increased duration of surgery, and being the first surgery of the day. *C. Acnes* infections are oftentimes challenging to diagnose, grow slowly in culture, require debridement, revision of implants, and prolonged antibiotic courses to clear from shoulder arthroplasties. Revision incisions through colonized skin may produce seeding of *C. Acnes* into the dermis and subcutaneous tissue. These deeper infections evade pre-operative eradication and can lead to functional immobility and chronic pain.

In recent years, topical methods of eradicating or reducing the skin burden of *C. Acnes* have been investigated, including chlorhexidine swabs and topical benzoyl peroxide (BPO) as oral antibiotics including doxycycline have not proven effective. Topical BPO has been shown in several studies to be superior to chlorhexidine in reducing bacterial load using swab cultures of the epidermis and deep sebaceous glands. However, several drawbacks of topical BPO have been described including bleaching of clothing, requirement for serial application leading to poor compliance, potential for irritant and allergic contact dermatitis, and inconsistency in eradicating *C. Acnes* in some reports. In addition, there is concern that topical treatments may not penetrate into the superficial dermal layers to eradicate bacteria colonizing 1 mm beneath the skin surface, where the sebaceous glands reside.

Blue light therapy, with wavelength 405nm-470 nanometers (nm), is an Food & Drug Administration (FDA) approved modality that has previously been described in the dermatology literature as a highly effective antimicrobial agent against *C. Acnes*, among other bacteria, in mild to moderate inflammatory acne patients. The benefit of blue light therapy is that a single treatment can kill 99.9% of *C. Acnes*. The anti-microbial mechanism of action involves absorption by endogenous porphyrins which induce generation of reactive oxygen species leading to cell death and DNA cleavage. In contrast to topical antimicrobials, blue light therapy penetrates to 1.2-1.5 mm beneath the skin surface to eliminate bacteria residing in the sebaceous glands. Blue light demonstrates bactericidal effects at doses as low as 5 J/cm^2, while higher doses (>100 J/cm^2) are necessary to injure human tissues. Wavelengths of 405-415 nm with a radiant exposure of 54 - 75 J/cm^2 have been demonstrated to exert the greatest antimicrobial effects against *C. Acnes*. Variables that affect radiant exposure include: power of the blue light device (W), desired surface area to be treated (cm^2), time duration of treatment (s). Devices with lower irradiances (W/cm^2) require treatment for a longer time duration (s) to

achieve adequate radiant exposure [energy (J)/area (cm^2)] for antimicrobial effects. Side effects of blue light are transient and mild, including dry skin and hyperpigmentation.

This proposal aims to investigate a novel light-based treatment to reduce morbidity in shoulder surgical patients. This has potential to improve outcomes and reduce health care utilization associated with infectious complications of shoulder arthroplasty.

#### **Limitations:**

- This study is not without limitations. *C. Acnes* is challenging to culture with samples needing to be held for approximately 2 weeks to ensure 95% sensitivity. In addition, there is no standard method for swabbing the skin to obtain cultures. There have been various methods described for how to swab technique when obtaining culture samples. The methodology used by Scheer et al was selected for the present study given the detailed description and was therefore, reproducible.

#### **Future Directions:**

- Subsequent investigations to evaluate the efficacy of blue light therapy for eradication of *C. Acnes* will include a randomized clinical trial in shoulder arthroplasty patients incorporating not only superficial cultures but deep cultures and synovial fluid analysis.
- Additional studies targeting the highest risk surgical patient population, revision arthroplasty cases, will be impactful. These studies should incorporate 2-year clinical follow-up complete with patient reported outcome measures to see if utilization of blue light therapy may be associated with diminished pain and dysfunction in those patients with culture negative work-up.
- Finally, blue light studies to date indicate promising applications beyond *C. Acnes* including activity against staph, strep, pseudomonas, and yeast. Future studies could focus on these species as sources of both prosthetic joint infection as well as blue light's role in treatment and preventing infection across multiple specialties.

#### **D: Preliminary Studies/Progress Report**

No preliminary studies have been conducted to date. This study will begin enrolling in July 2020 once the purchasing of all materials has transpired and all funding sources in addition to internal funding are secured.

#### **E: Research Design and Methods**

**Study Design:** Single-Blinded (investigators performing analysis), randomized controlled trial

**Study Participants/Human Subjects:** 60 volunteers

**Power Analysis:** Power analysis calculations were performed using G\*Power (Universität Kiel, Germany). With an  $\alpha$  of 0.05 and 90% power to detect a 50% difference in positive culture rates as previously described, it was determined that 51 total patients needed to be enrolled. For the purposes of the present study, assuming a 15% attrition rate, it was determined that 20 subjects per group, 60 subjects total, were necessary.

**Inclusion Criteria:** Healthy Male Volunteers at least 18 years of age

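### The 90% power is not tied to the Aim 1 comparison: 51 matches a three-group test, and blue light versus benzoyl peroxide at mid-range rates has about 79–88% power with 17 evaluable per arm

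*Combined protocol and SAP*

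**What the plan says.** Section E, Power Analysis, reports a G*Power calculation with an alpha "of 0.05 and 90% power to detect a 50% difference in positive culture rates", from which "it was determined that 51 total patients needed to be enrolled". Allowing for 15% attrition, this becomes 20 per group and 60 in total. Randomized Groups, in the same section, sets three equal groups: benzoyl peroxide (BPO), blue light, and both.

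Section A asks about particular arms. Aim 1 is "To determine if blue light therapy is superior to 5% topical benzoyl peroxide gel". Aim 2 is "To determine if blue light therapy has additive or synergistic effects in eradicating" the organism together with BPO. The Hypothesis covers the Aim 1 contrast alone: "Blue light therapy will result in fewer positive culture specimens than those treated with topical benzoyl peroxide".

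The power paragraph does not give the test, one- or two-sided testing, the culture rates behind the 50%, or which arms are compared. No analysis section elsewhere supplies these.

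**The concern.** A power statement belongs to one test of one comparison. A three-group test that rejects says only that some arm differs. It does not say that blue light differs from BPO. Aim 1 uses two of the three arms, so 34 of the 51 evaluable subjects.

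If 90% was computed for the three-group test, the Aim 1 comparison has less. A non-significant blue light v BPO result would then be read as coming from a 90%-powered comparison when the chance of missing the planned effect could be up to twice the stated 10%. The power paragraph is the plan's only statistical text, so nothing else corrects that reading.

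**Working it through.** **Inputs.** From Section E: alpha 0.05, power 90%, a 50% difference, N = 51, attrition 15%, three equal groups, hence 51/3 = 17 evaluable and 20 enrolled per arm. Assumed, because the plan is silent: two-sided testing, and the 50% read as 50 percentage points. The culture rates used below are also assumptions.

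**1. Reproduce 51.** Chi-square power is the probability that a non-central chi-square with non-centrality λ = N × w² exceeds the critical value. With w = 0.5 and 2 df (critical value 5.991):
- N = 50: λ = 12.50, power 0.896
- N = 51: λ = 12.75, power 0.902

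So 51 is the exact minimum, and 51/0.85 = 60 matches the enrolment figure.

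**2. Is that the only route to 51?** No. Pooled two-proportion sizing per arm, two-sided, is

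n = [1.96 √(2p̄(1−p̄)) + 1.2816 √(p₁(1−p₁) + p₂(1−p₂))]² / (p₁−p₂)²

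- 60% v 10% (90% v 40% is its mirror image): (1.322 + 0.736)² / 0.25 = 16.9, so 17 per arm and 3 × 17 = 51
- 75% v 25%: (1.386 + 0.785)² / 0.25 = 18.8, so 19 per arm and 57 in total

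**3. Put w = 0.5 into a two-arm test.** For two equal arms at 75% and 25%, w = 0.25/√(0.5 × 0.5) = 0.5. With 1 df (critical value 3.841):
- N = 34 (17 per arm): λ = 8.5, power 0.830
- N = 40 (20 per arm): λ = 10.0, power 0.885
- 90% needs N = 43 in the two arms

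**4. Other tests of Aim 1, two-sided 0.05.** Fisher and uncorrected chi-square figures come from exact enumeration of the two binomials.

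| Test | 75% v 25%, 17 per arm | 75% v 25%, 20 per arm | 60% v 10%, 17 per arm | 60% v 10%, 20 per arm |
|---|---|---|---|---|
| Fisher exact | 79.0% | 83.4% | 82.7% | 90.8% |
| 1-df approximation | 83.0% | 88.5% | – | – |
| Pooled z approximation | 86.5% | 91.7% | 90.1% | 94.4% |
| Uncorrected chi-square | 88.1% | 90.1% | 90.5% | 95.1% |

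Rates of 90% v 40% give the same figures as 60% v 10%. At 17 per arm, 70% v 20% and 80% v 30% give 79.2% (Fisher) and 88.3% (uncorrected chi-square). Two-sided Fisher is still at 88.4% for 55% v 5%, and reaches 97.5% at 50% v 0%.

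**5. One-sided 0.05, 17 per arm.** Fisher gives 88.1% at 75% v 25% and 90.5% at 60% v 10%. The pooled z approximation gives 92.9% and 95.1%.

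**6. The three-group effect is not the two-arm effect.** Across three equal arms, rates of 75/25/25 give w = 0.478 and omnibus power of 87% at N = 51. Rates of 75/50/25 give w = 0.408 and 75%. A 50-point spread therefore does not secure 90% for the omnibus test either.

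**The case against.** **The 90% may belong to Aim 1 after all.** Step 2 shows that pairwise sizing at 60% v 10% or 90% v 40% lands on 17 per arm with 90.1% power. The plan takes its 50% from cited studies whose rates it does not reproduce. This stands. A reader might infer that the sponsor demonstrably sized the wrong test, but the documents do not support that. They show only that the statement fails to identify its test, and that 51 matches an omnibus calculation.

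**The lowest figures depend on the test chosen.** This also stands. A reader might infer that power is 79–83%, with a one-in-five chance of missing the effect. That holds for Fisher or the 1-df approximation at w = 0.5. Uncorrected chi-square gives 88%, so at 75% v 25% the miss probability runs from about 12% to 21%. Both Aim 1 and the Hypothesis are directional, and a one-sided test would raise power further. The plan chooses neither.

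**Multiplicity.** A reader might infer that testing two aims at 0.05 each must inflate the false-positive rate. With a common rate of 30–70% and 17–20 per arm, two unadjusted chi-square tests give a family-wise error of about 8–10%, but two Fisher tests give about 4–5%. No test is named, so inflation cannot be asserted in general.

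**Aim 2 is not simply pairwise.** Combination v BPO addresses an added effect. Synergy is not a single two-arm contrast. The pairwise argument is therefore firm for Aim 1 and only partial for Aim 2.

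**Conclusion.** The concern holds as a defect in the power statement. The 90% is not attached to an identified comparison, and 51 is an exact match to a three-group test that does not answer Aim 1.

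For an absolute 50-point difference at mid-range rates (75% v 25%), tested two-sided at 0.05, Aim 1 power is 79–88% with 17 evaluable per arm. At 20 per arm, which requires no attrition, exact power just reaches 90% with the uncorrected chi-square (Fisher 83%). At 17 per arm, two-sided 90% needs rates of 60% v 10%, 90% v 40% or beyond with an uncorrected test. Fisher gets there only with an arm practically at 0% or 100%. One-sided, Fisher reaches 90% at 60% v 10% or 90% v 40%, and an uncorrected test does so at mid-range rates too.

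All of this takes the 50% as absolute. If it means a relative halving, Fisher power at 17 per arm is lower, from 21% (50% v 25%) to 73% (90% v 45%). The shortfall on the absolute reading is moderate and does not invalidate the design.

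**What to change.** Keep 60 subjects and revise the Power Analysis paragraph.

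- Replace the 90% statement with the power of the blue light v BPO comparison of treated shoulders at 17 evaluable and 20 enrolled per arm, naming the test, sidedness and both assumed culture rates. A model sentence, with rates for the sponsor to replace: with 17 evaluable (20 enrolled) per arm, a two-sided Fisher exact test at 0.05 has 79% (83%) power for 75% v 25% positive. If another test is chosen, give its figure.
- If 51 came from a three-group chi-square with w = 0.5, say so and label it as the omnibus figure. If it came from a pairwise calculation, state the rates.
- Name Aim 1 as the single primary test at 0.05, as the Hypothesis already implies. Test Aim 2 afterwards, or report it as an estimate with a confidence interval.

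The cost is a few sentences and a less favourable stated power. No subjects are added. By contrast, restoring 90% for 75% v 25% after 15% attrition would take 23 evaluable per arm by Fisher: 23/0.85 = 27.1, so 28 per arm and 84 in total.
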